Aim 2) As a pilot study, the analyses will not have adequate power to detect significant differences. Therefore, initial effect sizes, rather than statistical significance, will be examined for evidence of the effectiveness of the intervention. With a target sample size of 44, 22 in the waitlist control and 22 in the intervention, we will be able to gauge an initial estimate of the effect size associated with the intervention as compared to usual care for caregivers. Waitlist control groups are used to first provide an untreated comparison and second to allow wait-listed participants an opportunity to receive the intervention at a later date. ⁸⁷ This is especially appropriate given that very few services are currently offered to HF caregivers. We will also conduct debriefing interviews with all participants following the trial. To account for an estimated 20% attrition, we will recruit a total of 49 to the trial with the goal of 44 participants completing the study.

Understanding the factors that predict which intervention components are successfully implemented and for which participant subgroups will be critical for fine-tuning this multicomponent intervention for future proposals that will extend efficacy examinations and effect modification analyses. Acceptability of the intervention will be examined in multiple ways. We will examine percentages of people who stayed in each arm of the study and conduct numerous descriptive correlational analyses of the association between the intervention compliance and other variables. These analyses will quantify intervention implementation by demographic and participant health variables. Analyses that utilize the post-randomization data (e.g., treatment compliance) ⁴⁰⁻⁴³ will be evaluated in supplementary analyses. We will distinguish non-compliance with intervention from attrition or loss to follow-up, i.e., missing data. We will also use the participant satisfaction data to examine acceptability of the intervention.

d. Early stopping rules.

As this is a low-risk behavioral intervention pilot, we have not defined any early stopping rules.

8. Risks

Minimal risks to study participants are expected. Some participants may experience some discomfort or fatigue in study interactions or in answering questions about their caregiving. Interviewers and interventionists will be trained to handle these minimal discomforts if they should occur, offering opportunities to rest throughout the interviews and intervention sessions. There is a low risk of physical injury for participants that set goals related to physical activity. For participants that want to set a goal related to physical activity, the interventionist will assess current physical activities, weekly duration and intensity and the safety of physical activity with Physical Activity Readiness assessment. If participant answers "No" to all questions, they are cleared for physical activity and will set a moderate activity goal with the nurse interventionist. If the results of the Physical Activity Readiness Assessment tool do not clear the participant for physical activity, the nurse interventionist will contact the study nurse practitioner - [name], CRNP, FNP-BC - to determine the safety of the participant's physical activity goal. In addition, if results of the Physical Activity Readiness Assessment tool and/or guidance from the study

nurse practitioner suggest seeking further advice from a medical professional, a goal to schedule a primary care visit will be made in lieu of a physical activity goal to discuss a medically-supervised exercise plan.

Education in protection of human research participants: All investigators have completed the Johns Hopkins University School of Medicine Research Compliance course and have been certified to conduct human research. The course consists of the University of Minnesota Web modules on Informed Consent, the consent Process, and After Informed Consent, Johns Hopkins University School of Medicine module on local IRB requirements, and achievement of a passing score on the Johns Hopkins Knowledge Assessment module. According to the policies of the Johns Hopkins University, approval for this research will be obtained from the IRB office for research using human subjects prior to collecting data. Minorities and women are included in this study, and all data will be presented in group format. Participants will be assigned a code number on initial entry and all subsequent questionnaires will be identified only by code number. Information needed for follow-up contact (names and addresses) will be kept separately from all other data.

Procedures for protecting against and minimizing potential risks: The interviewer will notify the Principal Investigator (a nurse) of any concerns for distress related to the study and participants will receive a follow-up telephone call to assure that the mild distress has resolved. In situations where there is initial severe distress or when the distress has not been resolved, we will consult with our Co-Investigator, [name], FNP-BC. Furthermore, if any physical problems emerge during any of the study for either patients or caregivers, immediate medical attention will be sought for the participant. The research assistants will all be nurses and will be trained to call 911 if they have serious concerns of an emergent issue.

The risk of invasion of privacy will be addressed with participants during the informed consent process. All personnel involved in the study will be fully trained and certified in the protection of human subjects and HIPAA regulations. This certification will be kept current throughout the study. As part of the informed consent process, participants will be notified of their rights pertaining to protected health information. Participants will be informed that they can stop the questionnaire and rest at any time. All study participants will be provided referral information to existing health services as in typical or usual care. Thus, participants have the information to access any services that they may perceive as necessary independent of their study participation.

The risk of breaching study participant confidentiality will be minimized by identifying all participants by code numbers and securing all data collected in locked files in the PI's office and screening information to locked file cabinets with limited staff access. Pre-coded data collection instruments are prepared for use with study participants at each testing occasion. Identification numbers to assure subject confidentiality will be used. Only one master log of subject name, address and telephone number and study identification assignment will be maintained on site in the locked PI's office. This log, in both hard copy and electronic file saved to an encrypted USB drive, will be stored in a locked filing cabinet separate from other identifying information. All completed data collection instruments are stored in locked filing cabinets. Audio recording of screens, interviews, and intervention will be identified by numbers only and stored on the Johns Hopkins Secure Analytic Framework Environment (SAFE) virtual desktop of [name] who will provide fidelity oversight of the interventionists. Access to these computer files will be password protected, audio recordings will not contain respondent name or other personal identifying information. Recorded interviews and key stakeholder meetings will be transcribed by a transcription service, Production Transcripts, Inc. All recordings and transcripts will be password protected and stored on the Johns Hopkins SAFE virtual desktop. Each transcript will be redacted for identifiers prior to analysis. Audio recordings from intervention sessions will be used only for quality control and training purposes and then destroyed (deleted from computers) within one year of trial completion. We will use a virtual video call software, either HIPAA compliant Zoom or DoxyMe. DoxyMe is encrypted, collects no protected

health information (PHI) and any data transmitted during the call is destroyed when the call ends. It is both HIPAA and HITECH compliant (https://doxy.me/en/about/).

Data Safety and Monitoring: Investigators will use the REDCap data entry system. Deidentified data sets will be exported from REDCap for analysis. The study data will be stored in databases on the Johns Hopkins Secure Analytic Framework Environment (SAFE) virtual desktop. Data will be restricted to those with permission to access it. However, any paper copies of consents or other study data will be stored in locked file cabinets.

The PI will be responsible for reviewing the safety of study participants during the conduct of this study and provide recommendations to the research team on specific aspects of the research protocol as it pertains to safety, potential study alerts and adverse events. Specific responsibilities of the PI will be to a) provide monthly review of recruitment and enrollment progress; b) review adverse events (AEs) including serious events and offer recommendations regarding the trial based on such observed events; c) support the research team regarding study procedures to address ethical dilemmas (e.g., reporting of abuse), safety of subjects in the trial, and appropriateness of all study procedures. We will not conduct interim analyses for this pilot study.

Recruitment, Adverse Events (AE) and Alert Reports: Reports presented to the PI will include data on enrollment (study accrual by month; comparison of expected to actual enrollment; number of individuals screened, number eligible and number ineligible, number randomized by gender), AEs, and alerts. Also, the PI will receive reports of the number of study participants who discontinue from the treatment group and/or the study and reasons for discontinuation.

Adverse Event (AE) Reporting: The principal investigator is notified of any serious AE within 48 hours of initial notification to the project team. We do not anticipate any adverse reactions to the intervention. Based on our previous work and studies in this area by others, there is only a small risk that participants will become increasingly anxious as a consequence of the intervention and being involved in an active problem-solving, behavioral activation approach. However, interventionists will be well trained to manage this reaction or make an effective referral if necessary. Given that the study team may be in people's homes or able to see their homes by virtual video, there is the potential for a member of our research team to encounter a potential emergency situation that is not related to study participation (e.g., dehydration, environmental risk, medical emergency). We refer to such events as alerts and have well developed procedures for their management. However, the reporting of alerts to the IRB of JHU is not required (see Chart below of potential alert events and plan for their management and reporting).

Plan for reporting unanticipated problems or study deviations: There are only minimal risks associated with the trial. It is anticipated that participants will experience more benefits than risks from their participation in the trial.

Table 5: Specific Alerts and Actions Taken

| Alert | Action to be taken |
|--------------------------|--|
| Medical emergency: | If a JHU research staff person encounters this situation over the phone, the |
| • Chest pains | participant is put on hold and the research staff calls 911 immediately. If |
| • Excessive bleeding | situation occurs within home, then staff person calls 911 immediately, and |
| • Fall and cannot get up | stays with participant until help arrives. Research coordinator (RC) and PI |
| Difficulty breathing | are informed within 24 hours of the event. RC then contacts individual as a |
| | follow up within two days. Research staff member completes alert form and |
| | gives to RC (or designate) |
| Evidence of abuse | Evidence of physical abuse is as follows: |
| | Participant states to research staff that abuse occurs. |

| | • Research staff observes physical evidence (e.g., black eye, black and blue marks on arms/legs). |
|--|---|
| | Research staff member informs participant that a senior member of the research team will contact him/her later that day. Staff member informs RC immediately upon completion of interview or intervention session. RC (or designate) contacts participant to obtain further information. Participant is strongly encouraged to call his/her physician and/or Adult Protective Services (phone number will be provided). Based on the situation, the RC may notify Adult Protective Services. RC (or designate) completes Alert form. Note –The possibility of informing an agency about an abusive situation is stated in the informed consent. |
| Extreme Home Hazards | Research staff member notifies RC within 24 hours. RC (or designate) |
| Exposed electrical | completes Alert form. |
| External door missing | |
| or cannot be locked | |
| Ceiling, floors caved | |
| in | |
| • No temperature control (no air or heat; must be extreme) | |
| Major infestation | |

PI – Principal investigator; RC = Research Coordinator

Legal risks such as the risks that would be associated with breach of confidentiality: The risk of breaching study participant confidentiality will be minimized by identifying all participants by code numbers and securing all data collected in locked files in the PI's office and screening information to locked file cabinets with limited staff access. Pre-coded data collection instruments are prepared for use with study participants at each testing occasion. Identification numbers to assure subject confidentiality will be used. Only one master log of subject name, address and telephone number and study identification assignment will be maintained on site in the locked PI's office. This log, in both hard copy and electronic file saved to an encrypted USB drive, will be stored in a locked filing cabinet separate from other identifying information. All completed data collection instruments are stored in locked filing cabinets. Audio recording of interviews and intervention sessions will be identified by numbers only and stored on the Johns Hopkins Secure Analytic Framework Environment (SAFE) virtual desktop. Access to these computer files will be password protected, audio recordings will not contain respondent name or other personal identifying information. Recorded interviews will be transcribed by a transcription service, Production Transcripts, Inc. All recordings and transcripts will be password protected and stored on the Johns Hopkins SAFE virtual desktop. Each transcript will be redacted for identifiers prior to analysis. Audio recordings from intervention sessions will be used only for quality control and training purposes and then destroyed (deleted from computers) within one year of trial completion. We will use a virtual video call software, either HIPAA compliant Zoom or DoxyMe. DoxyMe is encrypted, collects no protected health information (PHI) and any data transmitted during the call is destroyed when the call ends. It is both HIPAA and HITECH compliant (https://doxy.me/en/about/).

Financial risks to the participants: There are no anticipated financial risks to the participants.

9. Benefits

Participants in the waitlist control group will not directly benefit during the waitlisted period of 12 weeks. Participants will receive study visits from a nurse when receiving the intervention.

10. Payment and Remuneration

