Therefore, we propose to develop and test a novel multi-component intervention tailored to caregiver goals, HEart failure Resilience Intervention for Caregivers (HEROIC), to improve preventive health behaviors, reduce caregiver burden and improve QOL among HF caregivers. The HEROIC intervention will include individualized, nurse-led sessions focused on a) a whole-person assessment, preventive health behaviors, personal goals, and purpose in life, b) discussion of caregiving in the context of the caregiver's identified 'purpose' which supports meaning-making and provides rationale for goal-setting to co-development of a plan to address caregiver goals to improve preventive health behaviors and/or reduce caregiver burden, and d) 'walking meetings' to model the importance of physical activity while discussing incremental action plans to help caregivers achieve goals. Because the caregiver prioritizes what matters to them, this approach will address the intersections of race, gender and financial strain by design.

The first phase of the study will be an open label pilot (N=5) followed by a single masked, two-group, randomized trial (N=44) to test the feasibility and gauge an initial effect size of the intervention. Participants will interact with study staff by phone or in-person for data collection and intervention visits, dependent on COVID-19 policies and the participants' preference. Participants will be randomized to either the immediate intervention group or the waitlist control group. In the waitlist control group, participants will receive usual care for the first 12 weeks (which is limited to printed materials provided in the clinic) and then begin the intervention. The intervention will consist of 5 individualized, nurse-led, home-based sessions, with telephone check-ins and text reminders, according to participant preference. Each participant will receive each intervention component, but interventionists will systematically tailor content to the participants' goals based on protocols. All participants will be reassessed at 12 weeks and 24 weeks by a research assistant (RA) masked to treatment condition. The primary outcome will be improvement in goal attainment of health behaviors, caregiver burden and QOL between baseline and 12 weeks. We will also examine the acceptability of the intervention using intervention compliance and participant satisfaction data.

2. Objectives

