| Week 10 | Discuss how caregiver will involve social support in next goals |
| | Walking meeting (if virtual: suggest participant take a walk during call) |
| Phone Check-in | Review/edit purpose statement |
| Week 12 | Assess goal attainment and strategies to achieve goal |
| | Walking meeting (suggest participant take a walk during call) |
| Data Collection Visit | Heartrate Variability Measurement |
| Week 12 | Survey |
| Data Collection Visit | Heartrate Variability Measurement |

Week 24 Survey

Death of the Patient: If the patient/care recipient of the enrolled caregiver/study participant dies during the study, we will send a sympathy card. In that communication, we will ask the caregiver if they would like to participate a modified version of the intervention for bereavement: 1-3 visits (scheduled every other week) with a nurse for bereavement support within two months of the death of the care recipient. Additional instrumental support resources will be suggested such as grief support groups, referral to Roberta's House and bereavement resources for tasks to complete after someone you love dies. If the caregiver chooses to discontinue their participation, we will discontinue study contact and data collection. Data from caregivers whose care recipient dies will be excluded from analysis of primary and secondary outcomes.

Research Variables and Measurement

We chose measures (Table 2) based on previous RCT experience of mentors as well as those that met the following criteria: 1) possess known reliability and validity with ethnically diverse samples; 2) are sensitive to change from an intervention; 3) have clinical relevance; 4) Common Data Elements to connect this work with the broader literature and 5) represent objective as well as subjective indicators of the domains we seek to impact. Finally, we sought to achieve a balance between psychometric quality and practical considerations such as respondent burden. All instruments with the exception of demographics will be measured at baseline, 12 and 24 weeks. Patient characteristics will be obtained from chart review.

^{*} Waitlist control group will begin intervention at week 12.

Table 4: Constructs, Instruments and Reliability

| Theoretical Construct | Instruments and variables | Cronbach's alpha | | | |
|--|--|---------------------|--|--|--|
| | Contextual Factors | | | | |
| | 1)How well does the amount of money you have take care | | | | |

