| Financial Strain | of your needs? 2)In general, how do your finances usually | - | | | |
| | work out at the end of the month? | | | | |
| Social Support | ENRICHED Social Support Instrument ⁶⁹ | 0.88 | | | |
| | Caregiver Characteristics | | | | |
| Demographics | Age, Race, Gender | - | | | |
| Depression | Patient Health Questionnaire (PHQ-8) ⁷⁰ | 0.86 | | | |
| Perceived Stress | Perceived Stress Scale ⁷¹ | 0.82 | | | |
| Co-morbidities | Charlson Comorbidity Index ^{72,73} | 0.81 | | | |
| | Patient Characteristics | | | | |
| Functional Status | New York Heart Association Class (chart review) | - | | | |
| Cognition | Mini-mental status exam (chart review) | - | | | |
| Co-morbidities | Charlson Comorbidity Index (chart review) ^{72,73} | 0.81 | | | |
| | Katz independence in activities of daily living ⁷⁴ (caregiver | | | | |
| Independence of Care | report) | 0.84 | | | |
| Recipient | Lawton instrumental activities of daily living ⁷⁵ (caregiver | 0.85 | | | |
| | report) | | | | |
| | Potential Mechanisms | | | | |
| Self-efficacy | Coping self-efficacy ⁷⁶ | 0.91 | | | |
| Resilience | Heart rate variability | - | | | |
| | Caregiver Outcomes | | | | |
| Goal Attainment: Preventive Health Behaviors | Goal Attainment Scaling ⁷⁷ | 0.91 | | | |
| C . D 1 | Oberst Caregiver Burden Scale ⁷⁸ | 0.00 | | | |
| Caregiver Burden | 2 domains: time caregiving and task difficulty | 0.90 | | | |
| | Modified Caregiver Strain Index ^{79,80} | 0.86 | | | |
| Quality of Life | NeuroQOL | 0.85 | | | |
| Quality of Life | RAND 36-Item Short Form Survey | | | | |
| | 1) "Since our last contact, were you seen at an emergency | | | | |
| Health care utilization | room or a medical facility (e.g., Urgent care) for outpatient | | | | |
| | treatment?" | - | | | |
| | 2) "Since our last contact, were you hospitalized, or did | | | | |
| | you stay in a hospital observation unit for any reason?"* | | | | |
| Fatigue | PROMIS Fatigue – Short Form | | | | |
| Family Function | Family Assessment Device - Global/General Functioning | | | | |
| | Scale | | | | |

^{*}adapted from the Atherosclerosis Risk in Communities (ARIC) study annual follow-up questionnaire for healthcare utilization

Data collection and management:

Data Collection:

1) Questionnaires - Baseline, 12 and 24-week data will be collected by research assistants masked to treatment assignment. All data will be entered into RedCap.⁸¹

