fidelity through records of home sessions (by date and duration), checklists completed by study team members and direct observations and discussions concerning intervention engagement to evaluate receipt, and enactment. Ten percent of sessions will be audio taped which will be reviewed by the research coordinator using a priori monitoring checklists developed for this trial. All data collection and intervention interactions will be recorded. Evaluation will include periodic assessments of data quality, participant recruitment, accrual, and retention. Feedback will be provided to each interventionist who will provide case presentations in supervisory sessions. Bi-weekly meetings of the nurse interventionist with the Research Coordinator, the PI, and [name] will assure on-going fidelity to the intervention.

Study duration and number of study visits required of research participants: Participation in the study will consist of initial study consent, baseline, 12 and 24-week data collection and 5 study interactions for the intervention. Based on participant preference, the nurse interventionist may also arrange phone calls between visits to assess progress towards goals.

Blinding, including justification for blinding:

Research staff performing outcome assessments will be masked to assignment. Prior to follow-up assessment, staff will use standardized language to instruct participants not to discuss their treatment allocation with staff.

Justification of why participants will not receive routine care or will have current therapy stopped: n/a

Justification for inclusion of a placebo or non-treatment group: Both groups will receive the intervention. We are using a waitlist design to have a comparison to usual care.

Definition of treatment failure or participant removal criteria: n/a

Description of what happens to participants receiving therapy when study ends or if a participant's participation in the study ends prematurely: n/a

5. Inclusion/Exclusion Criteria

Screening:

1) Six-Item Screener; Callahan CM et al., 2003

To be eligible for inclusion caregivers must:

- 1) 50 years or older and
- 2) English speaking
- 3) Live with the heart failure patient or visit the patient at least 3 days per week to provide care or support.
- 4) Provide support to the patient for at least 1 Instrumental Activity of Daily Living
- 5) Care for a heart failure patient hospitalized in the last 6 months

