Generalized estimating equations (GEE) will be used to examine the difference between intervention and waitlist groups in change from baseline to 12 and to 24 weeks for QOL (primary outcome). Time, group and the group by time interaction will be included in the model. We will also calculate Hedges' g for differences in change over time between the groups in change in primary outcomes. Hedges' g is recommended over Cohen's d' to correct of an upward bias in small sample sizes.⁸⁵ The effect size associated with the variables will be compared to established clinically significant improvement reported in the literature, rather than placing emphasis on statistical significance.

b. Secondary outcome variables.

Generalized estimating equations (GEE) will be used to examine the difference between intervention and waitlist groups in change from baseline to 12 and to 24 weeks for self-efficacy and HRV (secondary outcomes) using a similar approach (as described for primary outcome).

In addition, the correlation between the change in the mechanisms and change in primary outcomes will be examined. We will also examine cost of the intervention.

Mixed Methods Analysis - Qualitative analysis and joint displays will be used to compare those with improvement in quantitative outcomes after the intervention to those who did not have improvement to elucidate unmeasured or unpowered change as reported by participants. This mixed methods analytic approach to intervention evaluation maximizes what we will learn from the pilot by increasing understanding of context, responsiveness to ethnically and culturally diverse populations and how implementation influences outcomes. Thus, the development and testing of the HEROIC intervention will address preventive health behaviors of HF caregivers, using rigorous methods to

promote inclusivity and tailor the intervention to caregiver needs to decrease caregiver burden and improve quality of life.

c. Statistical plan including sample size justification and interim data analysis.

Sample Size:

Aim 1) For our open-label pilot we will include 5 caregivers to test intervention components, feasibility, acceptability, delivery and communication.

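### The bereavement exclusion has no time limit, so a patient death in weeks 12–24 removes a 12-week primary outcome that was already collected

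*Combined protocol and SAP*

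**What the plan says.** **The rule.** Section 4, Death of the Patient, is triggered by a death at any time in the study: "If the patient/care recipient of the enrolled caregiver/study participant dies during the study, we will send a sympathy card". It closes with the analysis rule: "Data from caregivers whose care recipient dies will be excluded from analysis of primary and secondary outcomes". Nothing there separates visits before the death from visits after it. Data collection stops only at the caregiver's choice: "If the caregiver chooses to discontinue their participation, we will discontinue study contact and data collection".

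**The primary outcome.** The overview before section 2 says: "The primary outcome will be improvement in goal attainment of health behaviors, caregiver burden and QOL between baseline and 12 weeks". Instruments are administered at baseline, 12 and 24 weeks.

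**The control period.** The footnote to Table 3 reads: "Waitlist control group will begin intervention at week 12".

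**The model.** Section 7, Aim 2, item a, specifies a GEE for change in QOL to 12 and to 24 weeks: "Time, group and the group by time interaction will be included in the model".

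**What section 7 leaves out.** It does not mention the death rule, defines no analysis population, and plans no analysis that brings these caregivers back.

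**The concern.** Some exclusion after a death is reasonable. The Oberst burden scale in Table 4 covers "2 domains: time caregiving and task difficulty", and those items have no referent once the patient has died. The protocol also offers bereaved caregivers a modified intervention, so later measurements reflect something other than the treatment under test.

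Neither reason reaches back to a visit completed while the patient was alive. A death in week 20 cannot change what was measured in week 12, yet the rule removes it. Whether a caregiver's 12-week outcome counts then depends on an event that follows its measurement. The 12-week effect is estimated only among caregivers whose patient survived to week 24.

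Deaths are foreseeable here. The protocol has a procedure for them, and the eligibility criteria require the caregiver to "Care for a heart failure patient hospitalized in the last 6 months". The main product of this pilot is an initial effect size from two arms of 22, so each lost record matters more than it would in a large trial.

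The rule also fits poorly with section 7, item c, which places analyses using post-randomisation information, such as compliance, in supplementary work. The death rule puts a post-randomisation condition into the main analysis.

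**Working it through.** The plan gives no figure to reproduce: it states neither patient mortality nor an expected number of exclusions. The first step is a reading check; the rest is illustration over an assumed range.

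**1. Reading check.** Take a caregiver assessed at baseline and week 12 whose patient dies in week 20.
- Death of the Patient: the death falls within the study, so the caregiver's data leave the primary and secondary outcome analyses.
- Overview: the baseline-to-12-week change is a primary outcome, and it is complete.
- Table 3 footnote: the waitlist arm is untreated until week 12, so the comparison is also complete.
- Section 7: a group-by-time GEE can use the baseline and week-12 records without week 24.

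The record is usable and is discarded.

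**2. Inputs.** N = 44, 22 per arm (section 7, sample size). Assumed: mortality over 24 weeks p = 5%, 10% or 15%, the same in both arms, with a constant hazard. Attrition is ignored.

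**3. Caregivers affected.** Survival to week 12 is √(1−p).
- Excluded by the rule: 44p
- Death before week 12: 44 × (1 − √(1−p))
- Death in weeks 12–24: 44 × (√(1−p) − (1−p))

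| p | Excluded | Before week 12 | Weeks 12–24 |
|---|---|---|---|
| 5% | 2.2 | 1.11 | 1.09 |
| 10% | 4.4 | 2.26 | 2.14 |
| 15% | 6.6 | 3.43 | 3.17 |

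A little under half of the exclusions follow a death after week 12.

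**4. Precision at week 12.** The 95% half-width for a standardised difference g, with n analysed in two equal arms, is 1.96 × √(4/n + g²/(2n)). Take g = 0.5. Under the rule n = 44(1−p); with pre-death outcomes kept n = 44√(1−p).

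| p | n, rule | Half-width | n, week 12 kept | Half-width | Gain |
|---|---|---|---|---|---|
| 5% | 41.8 | 0.616 | 42.9 | 0.608 | 0.008 |
| 10% | 39.6 | 0.633 | 41.7 | 0.616 | 0.016 |
| 15% | 37.4 | 0.651 | 40.6 | 0.625 | 0.026 |

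Gains are taken before rounding. Example at 10%, rule: 4/39.6 + 0.25/79.2 = 0.1010 + 0.0032 = 0.1042; √0.1042 = 0.3227; × 1.96 = 0.633.

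**5. Chance imbalance.** Let X₁ and X₂ be the caregivers lost per arm, independent Binomial(22, q). Under the rule q = p; with pre-death outcomes kept q = 1 − √(1−p) = 0.025, 0.051 or 0.078.

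| p | P(arms differ by ≥ 2), rule | P(arms differ by ≥ 2), week 12 kept |
|---|---|---|
| 5% | 28% | 13% |
| 10% | 44% | 28% |
| 15% | 52% | 38% |

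For scale, the plan's own 20% attrition put in as q gives 57%.

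**The case against.** **The effect is small.** The half-width narrows by roughly 1% to 4%, one to three records are at stake, and the pilot disclaims power and emphasises effect sizes. Nothing in the documents suggests that a caregiver intervention would alter patient deaths by arm, and if it does not, the exclusions balance in expectation. All of this stands, so the case rests on what the 12-week estimate means, not on power or demonstrated bias.

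**The imbalance figures are differences in counts, not bias.** They fall because fewer caregivers are removed, and ordinary attrition alone would give 57%. This also stands. They show only that the rule adds avoidable imbalance to what the design already carries.

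**The denominator is uncertain.** Section 7 presents 44 as the number completing after attrition and does not say whether its 20% attrition includes deaths. If 20% attrition also applied to the 44, the late-death counts would be 0.9, 1.7 or 2.5. The order of magnitude is the same.

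**Week 24 is also in the primary model.** Section 7 analyses change to both 12 and 24 weeks, whereas the overview names 12 weeks only. That difference does not rescue the rule, since the 12-week contrast is primary under either text and the model does not need a week-24 record to use week 12.

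**Only post-death data may have been meant.** The sentence does end a paragraph on bereavement. But its wording covers the caregiver's data without qualification, nothing elsewhere narrows it, and an analyst following it literally would drop the whole record.

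**Conclusion.** The concern holds. As written, the rule deletes valid 12-week outcomes because of deaths that come later, and section 7 neither narrows it nor restores the data. At an assumed 5% to 15% patient mortality over 24 weeks, constant hazard and 44 caregivers, about one to three completed 12-week outcomes are lost. The loss of precision is slight, and no differential bias is shown. The consequence is a 12-week estimate conditioned on survival beyond the time of measurement. This follows from the text alone; only the counts depend on the assumed mortality. The rule touches the primary and secondary outcome analyses, not the interview, acceptability or cost data. It should be corrected before analysis.

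**What to change.** Replace the exclusion sentence in section 4, and repeat the replacement in section 7, with:

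> Caregivers are analysed in the group to which they were randomised. Outcomes collected before the care recipient's death, including week 12, are included in the primary and secondary analyses; assessments after the death are not used in these analyses and are summarised separately. A sensitivity analysis excludes all caregivers whose care recipient died. Deaths are reported by arm and by period (before or after week 12).

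State as a limitation that caregivers bereaved before week 12 contribute baseline only. The offer of bereavement support is not at issue and needs no change.

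The cost is wording; no new data are needed. The change recovers only the late deaths, about half of those excluded, so it reduces the selection without removing it. An ordinary GEE will still treat visits missing after a death as missing completely at random, and the report should say so.
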